## PROCEDURES:

Recruitment. Participants will be recruited during PHP treatment. As standard clinical care, all patients are screened for smoking status upon admission. Current daily smokers will be informed about the study at that time and invited to be screened for participation. All women of childbearing potential who would like the nicotine patch will complete a pregnancy test prior to inclusion into the study. Eligible and interested participants will complete an enrollment/pre-quit visit while enrolled in the PHP, which includes a baseline assessment, random assignment to a condition, the first counseling session and 4 weeks of nicotine patches (to be started on the quit day). The enrollment visit can be on the same day as the first pre-quit visit counseling but doesn't need to be. Participants will then complete a second pre-quit counseling session (within one week of the pre-quit session but before discharge). If the participant is to be discharged before their first or second counseling session, the counselor will choose one of the following options in order of preference ((1) complete the second counseling session early but not on the same day as the first counseling session,(2) have the patient return to the partial hospital program location for the first or second counseling session, (3) complete the counseling session by phone and mail materials distributed during the counseling session). Following the second counseling session, participants will continue in their assigned post-discharge intervention consisting of up to 5 Quitline or ACT telephone sessions.

Study outcomes will be assessed at the end of the counseling treatment at an in-person visit 5 weeks after their visit 2 date OR 24 hours after the last counseling session by a research staff member, whichever is later. As an incentive for completion of the follow-up assessment, those in either group who complete this visit will receive \$20 compensation and an additional 4 weeks of the nicotine patch. We will try to schedule visits around existing appointments in the hospital system to increase compliance.

Randomization will use block randomization, unknown to the counselor or the participant. In order to balance any benefit of bupropion treatment in combination with the nicotine patch across treatment conditions, randomization will be stratified by bupropion use.

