## Interventions.

Nicotine patch. All participants will receive usual psychiatric care plus an offer of the nicotine patch (up to 8 weeks), dosed per package instructions. At the second pre-quit session, participants will be instructed on patch use. The first 4 weeks of patch will be distributed at enrollment and the second 4 weeks will be distributed at the follow-up visit.

Enhanced Usual Care (EUC). Participants in the EUC condition will receive one in-person counseling sessions during the PHP and a second telephone session the week following: the first session will occur prior to the quit day and will focus on establishing a quit plan and instructing the participant on the use of the nicotine patch; the second session will occur prior to quit day and will assess for any difficulties using the nicotine patch. After the second session, participants will be electronically referred to the RI state quitline. This quitline offers an enrollment call and 5 proactive counseling telephone counseling telephone calls to those who enroll. Quitline staff make up to 3 attempts per call to reach users. Total scheduled counseling time offered is 120 minutes. If the participant is unexpectedly discharged before their first counseling visit, the counselor will choose one of the following options in order of preference ((1) complete the second counseling session early but not on the same day as the first counseling session,(2) have the patient return to the partial hospital program location for the first counseling session, (3) complete the counseling session by phone and mail materials distributed during the counseling session).

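### Does an outcome visit with no latest date, tied to the last counseling session, need a new timing rule?

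*Protocol*

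**What the plan says.** The Protocol, Procedures (Recruitment), assesses outcomes in person at the end of counseling, "5 weeks after their visit 2 date OR 24 hours after the last counseling session by a research staff member, whichever is later". Counseling after session 2 consists of "up to 5 Quitline or ACT telephone sessions". On booking it adds: "We will try to schedule visits around existing appointments in the hospital system to increase compliance".

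Under Interventions, session 2 in Enhanced Usual Care (EUC) is "a second telephone session the week following". Participants are then referred to the state quitline: "This quitline offers an enrollment call and 5 proactive counseling telephone counseling telephone calls to those who enroll". It also says "Quitline staff make up to 3 attempts per call to reach users". ACT Care has one in-person contact and six by telephone.

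Table 2 and Measures place the outcomes at end of treatment, without a day number. The SAP describes all its analyses as descriptive. It reports abstinence by group with losses counted as smoking (Aim 2), psychiatric symptoms by group among completers and psychiatric rehospitalisation over the treatment period for the trial as a whole (Aim 1), and the ACT treatment targets before and after treatment (Aim 3).

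**The concern.** Three things are unwritten: a latest date for the visit, the meaning of *last* session, and the point at which someone is lost. The words about a research staff member can describe either the assessor or the person delivering the session. If they describe the session, the EUC visit stays at the 5-week floor while the ACT visit moves with its calls. If they describe the assessor, EUC timing follows an outside service that calls only those who enroll. Either way, assessment time can depend on what participants do after randomisation, and can do so differently by arm.

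Every outcome taken at the visit is exposed. Abstinence, symptoms and treatment targets could be measured at unequal times. Rehospitalisation would be counted over periods of unstated length. An undefined cut-off for loss affects both the abstinence rate, because losses count as smokers, and the retention figure that Measures compares with 80%.

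**Working it through.** **Inputs.** From the Protocol: a floor of 5 weeks = 35 days after visit 2; a 1-day wait after the last session; at most five calls after session 2 in either arm; a separate quitline enrollment call in EUC; 20 per arm, so 2 x 20 = 40; an 80% retention benchmark. Call spacing *s* is not stated, so equal spacing of 5, 7 or 10 days is assumed. The plan gives no power, alpha or effect size to reproduce.

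**Visit day.** With *n* calls, day after visit 2 = max(35, n x s + slip + 1). With no slip:

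| Spacing | Five calls (ACT, or EUC counting five) | EUC, enrollment call adds an interval | EUC, not enrolled or calls not counted | EUC minus ACT |
|---|---|---|---|---|
| 5 days | max(35, 26) = 35 | max(35, 31) = 35 | 35 | 0 |
| 7 days | max(35, 36) = 36 | max(35, 43) = 43 | 35 | -1 to +7 |
| 10 days | max(35, 51) = 51 | max(35, 61) = 61 | 35 | -16 to +10 |

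The floor stops governing once spacing exceeds 34/5 = 6.8 days with five calls, or 34/6 = 5.7 days with six. Weekly calls with one week's slip give 35 + 7 + 1 = day 43. If only ACT slipped and EUC stayed at the floor, the difference would be 35 - 43 = -8 days.

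**Which rows are plausible.** Five calls and a 5-week floor fit roughly weekly spacing; this is an inference. On that basis, with no slip, the difference is 0 or -1 day unless the enrollment call takes a full week of its own. The Protocol does not say that it does, and it lists that call apart from the five counseling calls.

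**Effect on outcomes.** One participant is 1/20 = 5 points of abstinence in an arm, and 1/40 = 2.5 points of retention (32/40 = 80.0%, 31/40 = 77.5%). These are the weight of one person under any problem and do not estimate this one. For rehospitalisation, assume 10% of 40 by the floor (4.0 people), a constant hazard, and all 40 visits 8 days late. Counted from session 1, taken as 1 to 7 days before session 2, the floor *d* is day 36 to 42. Then 40 x (1 - 0.9^((d + 8)/d)) = 4.83 for d = 36 and 4.72 for d = 42, less than one extra person. The SAP reports this count for the whole trial, so it is not an arm comparison.

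**The visit 2 anchor.** The sections disagree on whether session 2 is in person before discharge or by telephone. Either way it has a date. ACT's 1 + 6 = 7 contacts match two sessions plus five calls.

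**What a fixed day would cost.** A common day from randomisation = gap to session 1 + 7 + n x s + slack + 1. With a 3-day gap, five weekly calls and 7 days' slack (all assumed), this is 3 + 7 + 35 + 7 + 1 = day 53. A window of days 53 to 67 is 14 days wide, against a weekly spread of -1 to +7. The present floor on the same clock is 36 + 3 = 39 to 42 + 3 = 45, so the visit moves 8 to 14 days later.

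The second patch supply is given at this visit. The time between the end of the first 28 days of patches and the visit is visit day - 28 - quit day, both counted from visit 2. At the floor it is 6, 4 or 0 days for quit days 1, 3 or 7. At day 53, the visit is day 43 after visit 2 if session 2 is on day 10 (14, 12 or 8 days), and day 52 if session 2 is on day 1 (23, 21 or 17 days).

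**The case for a change.** The best argument for a change is that a descriptive plan is no defence. With no test, the reported rates are the result, and a reader needs to know when they were measured. The cap of five sessions and the limit of three attempts per call restrict counts, not calendar time. Weekly calls put the fifth on day 35, so any slip moves the visit. The documents do not say how staff would learn quitline call dates before booking. A closing date and a line on visit timing would cost little.

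Much of this stands. The latest date is absent, timing can follow attendance, and neither arm is guaranteed the same interval. What does not follow is that the stated rule is wrong. No direction of bias is shown, and the size rests on assumed spacing. The closing date and definitions are operating detail that a study team must settle in order to book and close visits. Days to assessment by arm can be computed from visit dates, since the rule itself requires the visit 2 date to be known. Replacing the rule with a fixed day removes the dependence on attendance, but gives up assessment after treatment ends and delays the visit.

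**Conclusion.** No change to the plan is needed. The rule fixes a clear earliest date and implements a stated choice to assess after counseling ends. What is missing is definitional detail that can be filled sensibly: one meaning of the last session for both arms, a closing date for counting someone as lost, and a report of visit timing by arm.

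Under weekly spacing, five calls and no slip, the arms differ by 0 or 1 day. Differences of +7 (weekly), or of -16 to +10 (10-day spacing), depend on spacing or an enrollment-call interval that the documents do not state. One week's slip confined to ACT would give up to -8 days. The effect on abstinence, symptoms and treatment targets is of unknown direction and cannot be computed from the documents. No error rate is involved. A fixed common day is a trade-off with no clear gain in a feasibility pilot of 40.

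Two neighbouring matters are separate. The descriptions of session 2 in Procedures and Interventions should be reconciled as a wording issue. The study team should also read the patch-supply statements against the visit timing; no view is taken here on supply.

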Several pilot studies show promise for ACT as a treatment for tobacco dependence, including one showing favorable results compared to traditional cognitive behavioral approaches. To date, no large scale (fully powered) trials have been completed on the use of ACT for tobacco cessation.

Most of the ACT for smoking cessation studies have included only non-psychiatric populations. ACT may be particularly well-suited for tobacco cessation in patients with psychiatric comorbidities as: (1) ACT treatments can also be applied to treat mental health symptoms allowing for a consistent treatment framework across diagnosis, (2) the hypothesized mechanism of change (i.e., willingness to experience distress and discomfort in order to live a valued life) may be particularly relevant for smokers with psychiatric comorbidities, who are more dependent and have more severe withdrawal symptoms (i.e., they will experience more

discomfort than average when quitting). There have been two, small, uncontrolled, feasibility studies of ACT for smoking cessation in patients with mental illness. These studies found ACT for tobacco cessation to be feasible in smokers with bipolar disorder and posttraumatic stress disorder. There have been no controlled trials of ACT for smoking cessation in patients with psychiatric comorbidities. More work is needed to assess the feasibility of applying the ACT treatment approach to tobacco cessation treatment with smokers with SMI, particularly among those in acute psychiatric episodes.

**SUBJECT RECRUITMENT:** Source. Participants will be recruited from the Rhode Island Hospital (RIH), Psychiatric Partial Hospitalization program (PHP; See letter from [name], Medical Director of the program). This day treatment program (8AM-2PM) employs the principles of ACT via four group sessions, and individual meetings with both a psychologist and a psychiatrist.

Sample size. We propose a sample size of 20 smokers per group because the primary aim of the R03 grant mechanism is to assess initial feasibility. We will oversample men such that 50% of the sample is male. Based on the current census of the PHP, we anticipate 240 smokers will be seen over the 8-month recruitment period, making it feasible to recruit 40 smokers.

Inclusion criteria. Participants will be male and female, current daily smokers,  $\geq$  age 18, have regular telephone access, and are able to read and write English.

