Counselor training. Counselors with previous experience in ACT will be trained by consultant [name] in the delivery of her ACT for smoking cessation protocol. [name] will review mock sessions of the counselors delivering the treatment and offer feedback to ensure that the counselors are trained to criterion. Counseling

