## 1. ADEQUACY OF PROTECTION AGAINST RISK

### Recruitment and Informed Consent

Participants who appear to meet inclusion/exclusion criteria, will be informed about the study by partial hospital program research assistants. If they express interest, they will be screened for eligibility criteria by the research assistants. At first contact, all participants will first be given a brief verbal overview of the study. If participants agree to be screened and pass the screening questions based on inclusion/exclusion criteria they will be invited to participate, and will complete a contact information form. The participant will then be scheduled for a baseline assessment visit and counseling session. Written informed consent (including a description of the nature, purpose, risks, and benefits of the study) will be obtained from participants before initiating the baseline assessment. The voluntary nature of the study and the participant's right to withdrawal at any time will be stressed during the consent process; this information will be provided to participants in written form at the time of consent. As part of the consent process, to ensure comprehension, following the participant reading the consent form, we will verbally explain the study to the participant. All participant questions will be answered prior to obtaining written consent. Research assistants and study counselors will obtain consent.

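### Study counselors may take consent although they learn the arm of each participant they treat, so under blocked allocation a consenting counselor may guess the next assignment better than chance

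*Protocol*

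**What the plan says.** The randomization paragraph under PROCEDURES in the Protocol holds the whole concealment plan: "Randomization will use block randomization, unknown to the counselor or the participant". The same paragraph adds that "randomization will be stratified by bupropion use". Neither document gives the block size, says whether it is fixed or varied, names who holds the list, or describes how an assignment is released.

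Under Recruitment and Informed Consent, research assistants tell patients about the study, and those interested hear that "they will be screened for eligibility criteria by the research assistants" is the next step: screening is a research assistant task. Consent is shared: "Research assistants and study counselors will obtain consent". Consent must precede the baseline assessment. The enrollment visit is described under PROCEDURES as one "which includes a baseline assessment, random assignment to a condition, the first counseling session and 4 weeks of nicotine patches".

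The arms are easy to tell apart for whoever delivers them. For the ACT arm, "Counselors with previous experience in ACT will be trained by consultant". In enhanced usual care the early sessions cover a quit plan and patch use, and then "After the second session, participants will be electronically referred to the RI state quitline".

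On size, the Protocol says "We propose a sample size of 20 smokers per group". The SAP limits itself to descriptive analysis. It reports sessions completed, satisfaction, psychiatric symptom means and abstinence by group, and Aim 3 addresses the effect of treatment condition on the ACT treatment targets.

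**The concern.** Hiding the list from counselors does not hide the assignments they have already delivered. In a permuted block each assignment changes the odds of the next, so someone who remembers recent assignments has an edge in guessing. That matters only if the same person can influence who enters and when. The consent section makes this possible, because a treating counselor may take consent from later participants.

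The influence need not be deliberate. A counselor who expects the next place to be ACT might encourage a motivated smoker a little more, or let an ambivalent one take longer to decide. The INFORMED CONSENT section lets patients take the form home and enroll later in their stay, so timing is flexible. Consent before randomization prevents re-assignment afterwards, but not this.

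With 20 per arm, one participant moves an arm's abstinence rate by 1/20 = 5 percentage points. A few steered enrollments could therefore color the comparison of arms on abstinence, sessions completed, satisfaction and treatment targets. The SAP describes no adjusted analysis that would offset this.

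**Working it through.** The documents state no predictability figure, so there is none to reproduce. The check asks how well a counselor could guess.

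**Inputs from the documents.** Two equal arms of 20, 40 in total (Protocol, SUBJECT RECRUITMENT); blocked allocation in two bupropion strata (PROCEDURES); counselors may take consent (Recruitment and Informed Consent).

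**Assumptions.** Block size 2, 4, 6 or 8; 10% or 25% of participants on bupropion; the guesser sees either all past assignments or a random half of them. The guesser always names the arm that is behind in that stratum and tosses a coin when the arms are level.

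**Step 1: block size known, all past assignments seen.** For a block of 2m, the expected share of correct guesses is [m + 2^(2m−1)/C(2m,m) − 1/2]/(2m).

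- Block of 2: (1 + 2/2 − 0.5)/2 = 1.5/2 = 75.0%
- Block of 4: (2 + 8/6 − 0.5)/4 = 2.833/4 = 70.8%
- Block of 6: (3 + 32/20 − 0.5)/6 = 4.1/6 = 68.3%
- Block of 8: (4 + 128/70 − 0.5)/8 = 5.329/8 = 66.6%

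The block of 4 can be checked position by position: (1/2 + 2/3 + 2/3 + 1)/4 = 70.8%. Full enumeration of the possible blocks gave the same four values.

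**Step 2: block size unknown.** The guesser uses only the running imbalance within each stratum. This was simulated for 40 participants, 20,000 times per setting.

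| Block size | Size known, all seen | Size unknown, all seen | Size unknown, half seen |
|---|---|---|---|
| 2 | 75.0% | 74% | 56% |
| 4 | 70.8% | 70% | 55–56% |
| 6 | 68.3% | 67% | 55–56% |
| 8 | 66.6% | 65% | 55% |
| 2 and 4 mixed | – | 71% | 56% |
| 4 and 6 mixed | – | 68% | 55–56% |
| 2, 4 and 6 mixed | – | 69% | 55–56% |

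The assumed share on bupropion made almost no difference.

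**Step 3: in participants.** Chance gives 0.50 × 40 = 20 correct guesses. Half sight gives about 0.55 × 40 = 22. Full sight gives 0.708 × 40 = 28.3 with blocks of 4 and 0.75 × 40 = 30 with blocks of 2.

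**Step 4: what changes the result.** Not knowing the block size costs the guesser only one or two points. Mixing block sizes leaves 68–71% when all past assignments are seen. Seeing fewer past assignments is what matters: half sight removes most of the edge. If the person taking consent has seen none, the figure is 50%.

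**The case against.** The strongest reply is that the exposure is narrow. Research assistants inform, screen and invite, and nothing gives counselors a say in whom to approach. A counselor who takes consent meets a patient already screened, interested and scheduled. The Protocol speaks of counselors in the plural without saying how many there are or whether each serves both arms, so a given counselor may see only part of the history. That points to the lower end of the range, a gain of about 5 or 6 points over chance. All of this stands, and it limits the concern to encouragement and timing at consent.

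A reader might infer more: that with blocks of 4 about 13 assignments are known in advance, since (1 + 1/3)/4 = 33.3% of them are certain and 0.333 × 40 = 13.3. The arithmetic is right but the documents do not support the inference. Certainty needs the block size, the block boundaries and every prior assignment in the stratum. The concealment sentence is most naturally read as hiding the block scheme from counselors.

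A reader might also infer that research assistants can foresee assignments because that sentence does not name them. Nothing shows that they learn the sequence or past assignments. The silence is missing detail, not a stated weakness.

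It is also fair to say that this is a 40-person pilot sized for feasibility, with no between-arm test, and that commitment to quitting and a dependence item are collected at enrollment, so gross imbalance on them could be seen. That lowers the stakes. It does not remove them, because the SAP still sets the arms side by side.

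**Conclusion.** The concern holds in a limited form. The Protocol lets a person who knows some past assignments take consent for later ones under blocked allocation, so that person may guess the next arm better than chance with the list hidden. Depending on how much of the history is seen and on block size, correct guessing lies between about 55% and 71%, or 75% with blocks of 2, against 50%. These figures rest on assumed block sizes and assumed visibility, since the documents give neither. They measure how guessable the next arm is. They do not show that selection would occur or how far any outcome would shift.

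The results exposed are the by-group figures: abstinence, sessions completed, satisfaction and treatment targets. Recruitment feasibility is not a between-arm contrast and is little affected. The change is worth making because it is cheap, but the point does not undermine the feasibility aim.

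**What to change.** In the Protocol's Recruitment and Informed Consent section, state that only research assistants who do not deliver counseling obtain consent. This is the change that matters.

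In the randomization paragraph under PROCEDURES, extend concealment of the sequence to everyone who screens or takes consent, and state that each assignment is released only after consent is signed and the baseline assessment is complete. The visit order already implies that timing; the sentence would make it binding. Guessing falls to 50% only if those taking consent also do not track past assignments, so the release should go to the counselor who needs it.

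Varying the block size is optional. It is not sufficient alone, as the 68–71% above shows.

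The cost is two sentences and some lost scheduling flexibility when only a counselor is on site. Research assistants already take consent, so no new role is needed. If enrollment is already complete, the report can instead state the block size, who held the list, how assignments were released and who took consent from each participant.
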